3.3 Subject Eligibility

This study intends to enroll patients with moderate heart failure and functional mitral regurgitation. All evaluations assessing eligibility criteria for this study must be performed within 45 days prior to randomization and the index procedure, unless otherwise noted.

All subjects will require informed consent for enrollment in this clinical study.

Many of the evaluations at eligibility will have been collected as part of a subject's standard chronic heart failure treatment regimen, prior to the subject being consented for the study. If these tests or examinations were completed as standard of care for the subject, and timing of the test or exam is within 45 days prior to randomization and the index procedure, the results are acceptable for use as satisfying eligibility requirements.

In cases when key evaluations have occurred more than 45 days prior to randomization, the subject must undergo new assessments for qualifying the subject for the clinical study.

3.3.1 Inclusion Criteria

The subject must meet **all** of the following criteria at the time of eligibility for randomization and the index procedure:

1. Diagnosis of dilated ischemic or non-ischemic cardiomyopathy
2. Functional Mitral Regurgitation:
2+ (Moderate), 3+ (Moderate/Severe), or 4+ (Severe)
3. NYHA II, III, or IV (refer to Appendix D for NYHA Classification)
4. Six Minute Walk distance of at least 150 meters and no farther than 450 meters
5. Subject meets anatomic screening criteria as determined by angiographic screening at the time of the index procedure to ensure that implant can be sized and placed in accordance with the Instructions for Use
6. Left Ventricular Ejection Fraction $\leq 50\%$
NOTE: Subjects with LVEF of 41- 50% can only be included if baseline NYHA is class III/IV **AND** MR grade is 3+/4+ (moderately-severe/severe)

7. LV end diastolic dimension (LVEDD) >55mm or LVEDD/BSA > 3.0cm/m²
8. Stable heart failure medication regimen for at least three (3) months (refer to Appendix G for definition of stable heart failure regimen)
9. Age ≥ 18 years old and ≤ 85 years old
10. The subject has read the informed consent, agrees to comply with the requirements, and has signed the informed consent to participate in the study
11. Female subjects of child-bearing potential must have a negative serum βHCG test

3.3.2 Exclusion Criteria

The following must **NOT** be present at the time of eligibility for randomization and the index procedure:

1. Hospitalization in past three (3) months due to myocardial infarction, coronary artery bypass graft surgery, and/or unstable angina
2. Hospitalization in the past 30 days for coronary angioplasty or stent placement
3. Subjects expected to require any cardiac surgery, including surgery for coronary artery disease (unprotected left main stenosis greater than or equal to 50% or, greater than or equal to 70% stenosis in at least three (3) epicardial coronary arteries in the absence of prior bypass surgery), or for pulmonic, aortic, or tricuspid valve disease within one (1) year
4. Subjects with echocardiographic documentation of non-compaction cardiomyopathy with associated hypercontractility of the cardiac structures supporting the mitral annulus
5. Subjects expected to require any percutaneous coronary intervention within 30 days of enrollment
6. Recipient of intravenous positive-inotrope infusion or intra- aortic balloon pump support within the past 30 days
7. Presence of a mechanical mitral heart valve, mitral bio-prosthetic valve or mitral annuloplasty ring
8. Pre-existing device (e.g., pacing lead) in coronary sinus (CS) / great cardiac vein (GCV), or anticipated need for cardiac resynchronization therapy (CRT) within twelve (12) months
9. Presence of a coronary artery stent under the CS / GCV in the implant target zone
10. Significant organic mitral valve pathology (e.g., moderate or severe myxomatous degeneration, with or without mitral leaflet prolapse, rheumatic disease, full or partial chordal rupture)
11. Presence of severe mitral annular calcification
12. Presence of left atrial appendage (LAA) clot. Patients with a current/ongoing (documented within the last 12 months) history of atrial fibrillation must undergo a

trans-esophageal echo prior to the procedure to rule-out left atrial appendage clot to minimize the risk of thrombo-embolism caused by the tissue plication

13. Cerebral vascular event within the past three (3) months
14. Presence of primary renal dysfunction or significantly compromised renal function as reflected by a serum creatinine > 2.2 mg/dL (194.5 µmol/L) OR estimated Glomerular Filtration Rate (eGFR) < 30 ml/min
15. Allergy to contrast dye that cannot be pre-medicated
16. Inability to undertake a six-minute walk test due to physical restrictions/limitations
17. Chronic severe pathology limiting survival to less than 12-months
18. Anticipated need of left ventricular assist device within twelve (12) months
19. Currently participating in an investigational study that clinically interferes with the current study endpoints.

3.4 Informed Consent and Study Enrollment

3.4.1 Informed Consent

To protect the rights and welfare of subjects, this clinical study will be conducted in conformance with ISO 14155:2011 Section 4 – Ethical Considerations.

The subject will be provided with ample time to read, ask questions as needed, be provided with all appropriate answers, and to understand the study before making decision to participate in the study or not.

For additional details on the Informed Consent process, please see section 7.1 – Informed Consent.

3.4.2 Enrollment and Eligibility

Once the subject has provided their consent, the subject is enrolled in the study.

Once the subject has completed the required baseline assessments and met all eligibility criteria (with the exception of the final anatomic eligibility), the subject can then be scheduled for angiographic/venogram to assess final eligibility prior to randomization.

Recruitment will continue in a consecutive manner until enrollment for the study is complete. In order to provide traceability for each subject enrolled in this study, unique study numbers will be assigned according to Cardiac Dimensions standard operating procedures, including study sites, study number, and a unique subject number.

3.5 Screening/Baseline Assessments

The following examinations and tests will be completed according to the schedule as shown. These will be completed prior to randomization and the index procedure for

those study subjects who continue to be eligible. This set of examinations and tests will be considered the study subject's baseline evaluations.

3.5.1 Not More than 45 Days Prior to Randomization

The following evaluations must be performed within 45 days prior to the index procedure. Subjects who continue to meet all of the inclusion and none of the exclusion criteria will be scheduled for randomization and the index procedure. Subjects who are found ineligible will be categorized as screen failures.

- Complete past medical history, physical exam (history to include details of original diagnosis and review of current and prior heart failure treatment)
- Transthoracic echocardiogram (TTE)
Note: Study sites that have experience and necessary equipment may undertake exercise echocardiography in addition to the standard resting echocardiographic assessment required by the protocol.
- Functional assessments:
 - NYHA Classification (reference Appendix D: NYHA Classification)
 - Six minute walk test. To minimize any training effect, the screening and baseline tests must be two separate assessments at least two hours apart (reference Appendix F: Six Minute Walk Test Protocol)
 - Kansas City Cardiomyopathy Questionnaire (KCCQ)
 - SF-12 Quality-of-Life Assessment Questionnaire
- Electrocardiogram (12-lead ECG)
- Serum chemistries: sodium, potassium, chloride, glucose, BUN, creatinine, and NT-BNP
- CBC with hemoglobin, hematocrit, platelets, and WBC
- Serum pregnancy test (if subject is a female of child-bearing potential)
- Other information to be recorded between eligibility and the study procedure:
 - Current medications
 - Adverse events including newly diagnosed infections, organ dysfunction, etc.

3.5.2 Not More than Three (3) Days Prior to Randomization

The following safety evaluations must be performed within three (3) days prior to the index procedure to ensure that subjects continue to be eligible for randomization and the index procedure:

- Vital signs: blood pressure, heart rate, respiratory rate, oxygen saturation, temperature, weight and height
- PTT and PT
- Cardiac enzymes: cardiac troponin (cTn)

- Serum creatinine
- Transesophageal echocardiogram (TEE) - to rule out left atrial appendage clot

Note: only required in subjects with existing atrial fibrillation.

Note: if TEE is done on the day of the study procedure and an LAA clot is identified (subject is ineligible), no study discharge evaluations are necessary. These subjects are regarded as screen failures.

3.5.3 Study Procedure - Prior to Randomization

3.5.3.1 Cardiac Catheterization Requirements

All subjects brought into the catheterization lab on the day of the index procedure will be pre-medicated according to institutional procedures for cardiac catheterization. Additionally, subjects will be heparinized prior to the angiographic procedure according to institutional policies. Anti-platelet therapy is not required in the trial, however, individual Investigators may prescribe such medications in accordance with their institution's standard of care or as necessary to treat other concurrent cardiac conditions. The use of anti-platelet therapy will be noted on the case report forms.

3.5.3.2 Eligibility Coronary Angiography

Coronary angiography will be performed immediately prior to randomization to confirm that the subject will not require percutaneous coronary intervention within 30 days from the time of randomization (Exclusion Criteria #5). At the Investigator's discretion, if the subject has:

- non-ischemic dilated cardiomyopathy - an arteriogram performed within twelve (12) months prior to eligibility assessment may be used to satisfy these criteria.
- ischemic dilated cardiomyopathy - an arteriogram performed within three (3) months prior to eligibility assessment may be used to satisfy these criteria.

If the Investigator determines that the eligibility angiography is not required on the day of the index procedure, the subject will minimally undergo femoral artery cannulation prior to randomization to obtain hemodynamic data and ensure that subject is blinded to the treatment assignment.

If the eligibility angiography reveals the need for revascularization, or if the study subject does not meet all eligibility criteria, the subject is an enrolled screen failure. Randomization does not occur and the subject is followed through discharge only.

3.5.3.3 Eligibility Venogram

A coronary sinus venogram will be performed immediately prior to randomization in order to assess eligibility for the study (Inclusion Criteria #5).

If the study subject does not meet the final venogram eligibility criteria, the subject is an enrolled screen failure. Randomization does not occur and the subject is followed through discharge only.

3.5.3.4 Fully Eligible Subjects

If the study subject meets all eligibility criteria, then the subject will be randomized. The test and evaluation results captured to date will become the study subject's baseline measurements.

3.6 Randomization

Randomization will occur in a 3:1 allocation to the Treatment (CARILLON) or Control group. Randomization will be stratified according to investigational center in a randomized permuted blocks design.

The study statistician will generate randomization schedules (independent of the Sponsor) and the randomization will be identified either through a web-based portal or by randomization envelopes provided for each center.

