4.1.4 Randomization

After all pre-randomization assessments have been completed, each subject will be assigned sequentially to one of the two study groups (Treatment or Control), by means of a computer-generated random number scheme created by the Sponsor (reference Section 3.6: Randomization). The study coordinator and limited study personnel (e.g., implanting physician) will also have knowledge of the treatment assignment.

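### Allocation concealment is not protected: per-center envelopes are allowed for center-stratified 3:1 blocks while unblinded sites still judge final eligibility

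*Protocol*

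**What the plan says.** **Method.** Protocol 3.6 sets a ratio of three Treatment subjects to one Control. On the structure of the list it says: "Randomization will be stratified according to investigational center in a randomized permuted blocks design". On delivery of the assignment, "the randomization will be identified either through a web-based portal or by randomization envelopes provided for each center". Section 6.4 repeats this. SAP 1.3.3 repeats the ratio and the center-stratified blocks, and speaks of the stratification as already done.

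**Who knows the assignments.** Protocol 4.1.4: "The study coordinator and limited study personnel (e.g., implanting physician) will also have knowledge of the treatment assignment". SAP 1.3.3 agrees. These people therefore know the sequence so far at their own center.

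**When eligibility is settled.** Inclusion criterion 5 (Protocol 3.3.1) reads in part "Subject meets anatomic screening criteria as determined by angiographic screening at the time of the index procedure". Section 3.5.3.3 adds: "A coronary sinus venogram will be performed immediately prior to randomization in order to assess eligibility for the study". Section 3.5.3.2 puts coronary angiography at the same moment and leaves the investigator some discretion over whether it is needed that day. A subject who fails either check becomes an enrolled screen failure and is not randomized.

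**Who makes the schedule.** Protocol 3.6 and 6.4 give this to the study statistician, independently of the Sponsor. Protocol 4.1.4 and SAP 1.3.3 say the Sponsor created the scheme.

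**Not stated in either document.** Block size, whether it varies, whether it is withheld from sites, how envelopes are sealed, numbered and logged, and whether eligibility must be entered before the assignment is released.

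**The concern.** Permuted blocks within a center become more predictable as each block fills, and at 3:1 there is one Control for every four places. Someone who knows the center's past assignments, and knows or guesses the block size, can sometimes work out the next one. In this trial such a person may be in the catheterization lab while final eligibility is still open and an exit without randomization is available. The Synopsis expects up to 180 consents to yield up to 120 randomized subjects, so exits before randomization are anticipated, although that difference also includes failures at baseline.

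If exits depended on the expected arm, the groups would differ before treatment. The core lab's masked reading (Protocol 4.2.2.1) protects the measurement of regurgitant volume but not the make-up of the arms. The primary test is an unadjusted comparison of change (Protocol 6.6, SAP 2.4.2 Primary Endpoint), so it would not correct such a difference. With 120 × 1/4 = 30 Controls randomized, a few selected entries could move the Control mean.

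Envelopes raise a different risk: one opened early reveals the assignment whatever the block size.

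**Working it through.** **1. The plan's own figure.** Difference 10 ml, SD 13 ml, two-sided 0.05, 3:1 (Protocol 6.6). SE = 13 × √(1/57 + 1/19) = 3.44 ml; noncentrality 10/3.44 = 2.90; 74 degrees of freedom; power 81.8%. With 54 + 18 = 72 it is 79.6%. The stated 76 (57 + 19) reproduces. Concealment does not enter this calculation, so 76 stands either way.

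**2. Inputs for predictability.** From the documents: 120 subjects, up to 25 centers (mean 120/25 = 4.8), 3:1, blocks within center. Assumed: a fixed block size that is known at the center. An assignment counts as certain when only one arm is left in the block. Layout: 20 centers of 5 and 5 centers of 4 (total 120).

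**3. Blocks of 4 (one Control).** With the Control in place 1, 2, 3 or 4, the number of certain Treatments is 3, 2, 1 or 0 (mean 1.5). In the last case the Control itself is certain (mean 0.25). That is 1.75 per block. A fifth subject opens a new block and adds none.
- 25 × 1.75 = 43.75; 43.75/120 = 36.5%
- Treatment: 37.5/120 = 31%. Control: 6.25/120 = 5%

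**4. Blocks of 8 (two Controls, 28 arrangements).** Places 3, 4 and 5 are certain with probability 1/28, 3/28 and 6/28. Sums: 10/28 for a center of 5, 4/28 for a center of 4.
- 20 × 10/28 + 5 × 4/28 = 7.86; 7.86/120 = 6.5%
- All are Treatment. A certain Control would need six Treatments first.

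**5. Blocks of 12 (three Controls, 220 arrangements).** Places 4 and 5: 1/220 and 4/220.
- 20 × 5/220 + 5 × 1/220 = 0.477; 0.477/120 = 0.4%

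**6. Sensitivity to center layout.** SAP 1.3.1 and 2.2 give up to 20 centers, so 6 subjects each. The uneven layout is an assumption: 5 centers of 12, 6 of 6 and 12 of 2.

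| Block size | 25 centers, 4–5 each | 20 centers, 6 each | Uneven |
|---|---|---|---|
| 4 | 36.5% | 2.0/6 = 33.3% | 41.25/120 = 34.4% |
| 8 | 6.5% | (20/28)/6 = 11.9% | 16.43/120 = 13.7% |
| 12 | 0.4% | (15/220)/6 = 1.1% | 13.16/120 = 11.0% |

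**7. What selection could do (illustration only).** Assume subjects in every certain Treatment place are 0.25 SD (3.25 ml) better and those in every certain Control place 0.25 SD worse. No passage supports that size. On the 25-center layout (90 Treatment, 30 Control), bias = 3.25 × (certain Treatment/90 + certain Control/30):
- Blocks of 4: 3.25 × (37.5/90 + 6.25/30) = 2.0 ml
- Blocks of 8: 3.25 × 7.86/90 = 0.28 ml
- Blocks of 12: 3.25 × 0.477/90 = 0.02 ml

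With SE 3.44 ml and 57 + 19 evaluable, two-sided type I error becomes about 9%, 5.1% and 5.0%.

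**The case against.** The strongest reply is that a reader might infer that the implanting physician does foresee assignments and selects on them. The documents do not support that reading.
- Certain foresight needs a block size that is fixed and known or guessable. Leaving it out of a protocol that sites receive is compatible with good concealment.
- No passage says the implanting physician personally makes the venogram call. The criterion is anatomic and tied to the Instructions for Use, so how much judgement it involves cannot be told from these documents.
- No passage says envelopes can be re-ordered, and they are one of two options. Silence on sealing, numbering and logging does not mean these are absent.
- Eligibility before assignment is already required (Protocol 3.5.3.4, 4.1.4), recruitment is consecutive (3.4.2, 7.8), late exits are a recorded category (3.7.2), and all subject records are source-verified (7.6.1.3).

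All of this stands as a limit on the claim. It is also true that the percentages measure block predictability, which a portal alone leaves unchanged, and that in the blocks-of-4 case most certain places are Treatment, where the prior chance was already 75%.

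The reply does not show that concealment is protected. Consecutive recruitment and source verification can expose selective exits afterwards but do not prevent them. Requiring eligibility first does not help if the next assignment can be seen or deduced while eligibility is being judged.

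**Conclusion.** The point holds as a weakness in protection, not as evidence of bias. Per-center envelopes, known past assignments and a site eligibility call immediately before randomization appear together, with no stated barrier between them. The block size left unstated would, taken alone, be only missing detail. The either/or on envelopes is more than that, because the plan already names a better method.

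The size depends wholly on the block size. At 4–5 subjects per center it is about 37%, 7% or 0.4% of assignments certain in advance for fixed, known blocks of 4, 8 or 12. Uneven recruitment raises the last two to about 14% and 11%. These figures leave out better-than-chance guessing. The envelope risk is separate and unquantified. The effect on the endpoint is not known; the 2.0 ml to 0.02 ml illustration rests on an assumed selection shift.

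The contradiction over who creates the schedule needs no assumption. It bears on concealment because a Sponsor field technician supports the procedure (Protocol 3.7.1.1).

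**What to change.** 1. In Protocol 3.6 and 6.4, strike the envelope option and use the web portal only. Release the assignment after final angiographic and venographic eligibility has been entered and locked.
2. For schedules not yet generated, use randomly varying block sizes, held in a restricted document and withheld from sites and Sponsor field staff. This addresses block-based foresight, which the portal alone does not. Residual predictability should be checked for the chosen mix, because a mix with many small blocks could keep much of it.
3. Keep the center strata.
4. Reconcile Protocol 3.6 and 6.4 with Protocol 4.1.4 and SAP 1.3.3 on who creates and holds the schedule.
5. If randomization is complete, as the SAP's wording may suggest, report the block sizes and which centers used envelopes, so that readers can judge concealment.

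The cost is small. The portal is already foreseen and the required 76 evaluable subjects do not change. Portal access is needed in every catheterization lab, balance within a center is slightly looser, and any schedules already made would have to be regenerated if the new block sizes were to apply to them.

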3.7 Study Procedure – Post Randomization

3.7.1 Index Procedure

3.7.1.1 Sponsor Support of Procedure

Cardiac Dimensions will provide a trained field clinical technician to support the investigational team during the procedure. Cardiac Dimensions may additionally provide a physician proctor, as needed.

3.7.1.2 Treatment Group

For subjects randomized to the Treatment group, the CARILLON Mitral Contour System procedure will be performed. The implant procedure is described in Appendix A: Instructions For Use.

Pre-medication will be according to institutional procedures for cardiac catheterization. Additionally, subjects will be heparinized prior to the angiographic procedure according to institutional policies. Anti-platelet therapy is not required in the REDUCE FMR Trial, however, individual Investigators may prescribe such medications in accordance with their institution's standard of care or as necessary to treat other concurrent cardiac conditions. The use of anti-platelet therapy will be noted on the case report forms.

Either Transesophageal Echocardiogram (TEE) or Transthoracic Echocardiogram (TTE) may be used during the implant procedure to evaluate the safety and effectiveness of device placement. If TEE is used during the index procedure, the assessment of the left atrial appendage clot exclusion criteria (required for subjects with existing atrial

fibrillation) may be made immediately prior to randomization and the index procedure (i.e., a separate TEE is not required.)

All subjects randomized to the Treatment group will have coronary angiography performed prior to the CARILLON implant attempt. This is in order to establish the baseline flow characteristics of the coronary arterial vessels in the same location (AV groove) as the coronary sinus/great cardiac vein. If coronary artery flow compromise is noted during the CARILLON implant procedure, the CARILLON device can be recaptured. At the investigator and proctor's discretion, another CARILLON device attempt can occur if the device can be placed in a portion of the coronary sinus/great cardiac vein where coronary flow is not compromised.

However, if there is **clinically significant** coronary artery compromise, mitral stenosis, systolic anterior motion or other safety issues, the CARILLON implant will be recaptured and the procedure ended.

If the patient becomes hemodynamically unstable and/or no CARILLON device implant is attempted, the subject will be classified as a Procedural Screen Failure in the Treatment group and will be followed through 1-month with a safety assessment only (full 1-month follow-up assessments are not necessary), then exited from the study.

If CARILLON device implant attempt(s) occur but the CARILLON device is ultimately recaptured and no implant takes place, the subject is classified as Non-implanted in the Treatment group and will be followed through the 12-month primary endpoint.

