3.7.2 Study Subject Follow-up Categories

SCREEN-FAILURE → Subject consented but did not meet baseline eligibility criteria (including TEE, if applicable). No study discharge evaluations are necessary.

ENROLLED SCREEN-FAILURE → Subject consented, met all baseline eligibility criteria, but did not meet final angiographic eligibility. Implant was not attempted. Limited study discharge evaluations are necessary, but no follow-up visits are required.

PROCEDURAL SCREEN-FAILURE → Randomized to treatment group, but procedure discontinued before an implant attempt. Full study discharge evaluations are required and the subject is followed through 1-month.

NON-IMPLANTED → Randomized to treatment group, implant attempted, but not successful. Full study discharge evaluations are required and the subject is followed through 12-months.

IMPLANTED → Randomized to treatment group, device successfully implanted. Full study discharge evaluations are required and the subject is followed through 12-months.

CONTROL → Randomized to control group, implant not attempted. Full study discharge evaluations are required and the subject is followed through 12-months.

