3.7.3 Discharge Evaluations

3.7.3.1 Randomized Subjects

Immediately following the index procedure, all randomized subjects will be observed overnight for complications related to the final eligibility assessments and/or procedure. This includes Procedural Screen Failures, Treatment subjects (non-implanted and implanted) and Control subjects.

Prior to hospital discharge, the following assessments will be performed:

- Physical examination
- Vital signs
- Abbreviated Echocardiogram (TTE) safety assessment
- Chest X-ray (PA and lateral) or cine fluoroscopy (for assessment of pulmonary congestion and assessment of implant integrity in implanted subjects)
- ECG (12-lead)
- Serum creatinine
- NT-BNP
- Cardiac enzymes: cardiac troponin (cTn)
Cardiac enzymes will be monitored 6-8 hours post procedure (or the following morning if procedure time was late in the day). If a clinically significant elevation in cardiac enzymes is noted then a repeat measurement should be undertaken for confirmation.
- CBC with differential, includes hemoglobin, hematocrit, platelets, and WBC
- Clinical assessments by the physician and other information to be evaluated and recorded as they occur including:
 - Concomitant medications
 - Adverse events

If the index procedure was discontinued before a CARILLON implant was attempted in a Treatment group subject, they are considered a Procedural Screen Failure and are followed through discharge and 1-month (safety assessment only), then exited from the study.

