3.7.3.2 Enrolled Screen Failures

The following safety evaluations will be performed prior to discharge for subjects who were brought into the catheterization lab but **do not** meet final eligibility criteria or for any other reason device implant is not attempted:

- Vital signs
- ECG (12-lead)
- Serum creatinine
- Cardiac enzymes: cardiac troponin (cTn)

Enrolled screen failure subjects are followed through discharge and then exited from the study.

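### A Treatment subject who becomes hemodynamically unstable at or after an implant attempt is exited at 1 month under one sentence of the protocol and followed to 12 months under others

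*Protocol*

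**What the plan says.** Protocol 3.7.1.2 sets out what happens to Treatment subjects in the catheterization laboratory. One sentence reads: "If the patient becomes hemodynamically unstable and/or no CARILLON device implant is attempted, the subject will be classified as a Procedural Screen Failure". It adds that such a subject "will be followed through 1-month with a safety assessment only" and is then exited. The paragraph that follows reads: "If CARILLON device implant attempt(s) occur but the CARILLON device is ultimately recaptured and no implant takes place, the subject is classified as Non-implanted", with follow-up to the 12-month primary endpoint. It makes no exception for instability.

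Protocol 3.7.2 lists the follow-up categories. Procedural Screen Failure is "Randomized to treatment group, but procedure discontinued before an implant attempt", with 1-month follow-up. Non-implanted is "Randomized to treatment group, implant attempted, but not successful", with 12-month follow-up. Implanted subjects are also followed for 12 months. Instability appears in none of these definitions. Sections 3.7.3.1 and 3.8.1 repeat the 1-month exit and tie it only to stopping before an attempt. SAP 2.3.2 uses the same attempt-based test to decide who leaves its ITT set.

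Protocol 3.7.3.2, headed Enrolled Screen Failures, gives a shorter set of discharge tests to subjects brought to the laboratory who do not "meet final eligibility criteria or for any other reason device implant is not attempted", and exits Enrolled Screen Failures at discharge.

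**The concern.** The conflict covers one definable group: Treatment subjects who become unstable during or after an attempt. If the device is recaptured, the subject meets the instability sentence (exit at 1 month) and the Non-implanted definition (12 months). If the device is left in place, the instability sentence taken literally still applies, against the 12-month rule for Implanted subjects.

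The 1-month route has consequences for the data:

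- **It is one-sided.** It exists only in the Treatment arm, since 3.7.2 follows Control subjects to 12 months. It also selects subjects on a complication of the procedure.
- **Exit ends data capture.** Protocol 5.1 and 5.1.2 collect adverse events only up to the last study visit. The 12-month major adverse event and heart failure hospitalization endpoints (3.2.2.1) and 12-month mortality (3.2.3) would be incomplete for these subjects.
- **The primary endpoint is missing.** Protocol 6.2 and SAP 2.1.1 leave subjects without 12-month data out of the primary analysis.
- **The LOCF analysis may not recover them.** Section 3.7.1.2 waives the full 1-month assessments, and the discharge echo in 3.7.3.1 is an abbreviated safety study. There may be no post-baseline regurgitant volume to carry forward.

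**Working it through.** **Rules side by side**

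| Treatment subject | 3.7.1.2, instability sentence | 3.7.1.2 next paragraph and 3.7.2 | Conflict? |
|---|---|---|---|
| Unstable before any attempt | Procedural Screen Failure, 1 month | Procedural Screen Failure, 1 month | No |
| Stable, no attempt | Procedural Screen Failure, 1 month | Procedural Screen Failure, 1 month | No |
| Unstable, attempted, recaptured | Procedural Screen Failure, 1 month | Non-implanted, 12 months | Yes |
| Unstable, implanted | Procedural Screen Failure, 1 month (literal reading) | Implanted, 12 months | Yes |
| Stable, attempted, recaptured | Not triggered | Non-implanted, 12 months | No |

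The conflict occupies the two rows where instability and an attempt occur together.

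**Effect on primary power**

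Inputs from Protocol 6.6: two-sided 0.05, 80% power, difference 12.4 − 2.4 = 10 ml, SD 13 ml in both groups, 3:1 allocation, Student's t test. The noncentrality is 10 / (13 × √(1/n_T + 1/n_C)), with n_T + n_C − 2 degrees of freedom.

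- The plan's figure: 57 and 19 gives power 81.8%, while 54 and 18 gives 79.6%. The stated 76 reproduces as the smallest exact 3:1 total reaching 80%.
- Expected evaluable: 120 × 3/4 = 90 Treatment and 30 Control. After the 30% attrition in 6.7, 90 × 0.7 = 63 and 30 × 0.7 = 21, with power 85.5%.
- Five more Treatment subjects lost (58 and 21): 84.7%.
- Fourteen more lost (49 and 21), which is the whole 15% non-implant allowance of 0.15 × 90 = 13.5, rounded up: 82.8%.

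These figures hold the 10 ml difference fixed.

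**Effect on the estimated difference**

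Section 6.6 takes −14.1 ml from the earlier implanted cohorts and −2.4 ml for subjects without an implant, with 15% not implanted. For 90 Treatment subjects that is 76.5 implanted and 13.5 not:

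- All counted: (76.5 × −14.1 + 13.5 × −2.4) / 90 = −1111.05 / 90 = −12.35 ml, close to the plan's −12.4.
- One non-implanted subject missing: (−1078.65 + 12.5 × −2.4) / 89 = −1108.65 / 89 = −12.46 ml.

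Each non-implanted subject dropped moves the expected Treatment mean by about 0.11 ml in the device's favour, before other attrition. For an unstable subject who was implanted, the documents give no basis for predicting the direction.

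**Effect on safety rates**

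One event missed after month 1 is 1/90 = 1.1 percentage points of the Treatment rate. SAP 2.3.2 keeps attempted subjects in its ITT set, and the event-table layout in SAP 4.3.1 divides by the total number of patients. A subject exited at 1 month without an event would then count as event-free to 12 months. The documents give no expected 12-month rate. The earlier 30-day rates of 1.9%, 2.8% and 13% (1.3.6) show only the scale on which 1.1 points would be read.

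**The case against.** The strongest reply is that the documents mostly point one way. Sections 3.7.2, 3.7.3.1 and 3.8.1 and SAP 2.3.2 all rest on whether an attempt was made. Within 3.7.1.2, the paragraph before the instability sentence already covers recapture for safety reasons, and the paragraph after it classes recaptured subjects as Non-implanted. On that view, one loose conjunction stands against several consistent statements. The reply also notes that section 1.3.6 attributes non-implantation in the earlier studies to access problems, coronary compromise and, in two of them, insufficient acute reduction of regurgitation. It names hemodynamic instability in none.

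Much of this stands. The attempt-based reading is probably the intended one, and the number affected may be zero. But the and/or is explicit, and it sits in the operative instructions for the Treatment procedure. A site that follows it is following the protocol.

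Four stronger readings are tempting but not supported:

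- **That every unstable Treatment subject faces two rules.** Instability before any attempt is consistently a 1-month exit.
- **That 3.7.3.2 is a third rule exiting randomized subjects at discharge.** Its wording is loose enough to suggest this. However, its heading and exit sentence name Enrolled Screen Failures. Section 3.7.2 defines them by failed angiographic eligibility, which 3.5.3 places before randomization. Section 3.7.3.1 says of its own, fuller discharge evaluations: "This includes Procedural Screen Failures, Treatment subjects (non-implanted and implanted) and Control subjects". Sections 3.7.3.1 and 3.8.1 then keep Procedural Screen Failures to 1 month.
- **That patients harmed in the procedure are lost altogether.** Overnight observation, discharge evaluation and a 1-month safety assessment are required under either reading.
- **That the number can be sized from the 15% allowance.** That needs an assumed share of unstable subjects, for which the documents offer nothing.

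**Conclusion.** The contradiction is real but narrow. It applies to Treatment subjects who become unstable at or after an implant attempt, and it gives them exit dates of 1 month and 12 months. If the instability sentence is applied literally, the 12-month regurgitant volume and the safety data after month 1 are lost in one arm, for subjects selected on a procedural complication.

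The case rests on possible bias and on completeness of 12-month safety data. Power is not the issue: it stays above 80% even if 14 further Treatment subjects are lost. The shift in the primary estimate is about 0.11 ml per non-implanted subject, which relies on the plan's own assumption that such subjects behave like Control. Each missed late event is worth 1.1 percentage points, assuming 90 Treatment subjects. How many subjects are affected is unknown, and zero is possible. The point merits correction because the rule is written down and works in one direction of selection; it does not by itself threaten the primary result.

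The SAP's removal of non-attempted subjects from ITT, against Protocol 6.2, is a separate matter and is not relied on here.

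**What to change.** Reconcile the instability sentence in 3.7.1.2 with the paragraph after it and with 3.7.2, 3.7.3.1 and 3.8.1, so that each randomized subject has exactly one follow-up category. One way is to let Procedural Screen Failure depend only on whether an implant was attempted, as 3.7.2 already does. Attempted subjects would then stay in data follow-up to 12 months whether or not they became unstable. As a minor clarification, limit the catch-all phrase in 3.7.3.2 to subjects who were not randomized.

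If follow-up has already ended, the sponsor should list each Treatment subject who became unstable at or after an attempt, with the category assigned and the exit date, so that the size of the problem is known.

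This concerns data follow-up only; no rule for clinical management is proposed. The cost is a protocol amendment, which section 7.5 sends to ethics committees and the regulatory authority for approval, and a few extra visits for any subjects concerned.
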